#### 4.6.2 Laboratory Safety Variables

Hematology, chemistry, urinalysis, and pregnancy testing samples will be drawn at the timepoints as described in the Schedule of assessment (SoA) ([Appendix 11.1](#)) and analyzed at central laboratories.

Hematology	Serum chemistry a	Urinalysis b
Red blood cell count	Total protein	pH
Hemoglobin	Albumin	Glucose
Reticulocyte %	Alkaline phosphatase	Protein
White blood cell count	Total bilirubin	Blood
Neutrophils %	Aspartate aminotransferase	Ketones
Neutrophils	Alanine aminotransferase	Nitrite
Lymphocytes %	Lactate dehydrogenase	Leukocyte
Lymphocytes	Sodium	Urobilinogen
Monocytes %	Potassium	Bilirubin
Monocytes	Chloride	Specific gravity
Eosinophils %	Urea/ blood urea nitrogen	
Eosinophils	Creatinine	
Basophils %	Calcium	
Basophils	Phosphate	
Platelets	Glucose	
Other tests		
HBsAg		
HBsAb		
HBcAb		
HCV antibody		
HIV antibody		
QuantiFERON-TB Gold or an equivalent test		
Pregnancy test (women of childbearing potential only) c		
Serum tryptase d		

- a) Fasting is recommended but not mandatory. The status of fasting or non-fasting should be recorded in the study source document.
- b) If any abnormalities are found in urinalysis, then microscopy should be conducted to examine the red cells, white cells, bacteria, casts, and crystals.
- c) Serum hCG will be performed at the Screening, Baseline (Day 1), Week 2 (Day 15), Week 4 (Day 29) visits, and at selected follow-up visits (including the extended follow-up). In addition, urine pregnancy test must be performed prior to dosing at Baseline (Day 1), Week 2 (Day 15) and Week 4 (Day 29) visits.
- d) For diagnostic purposes, any participant who experiences any systemic infusion-related event should have a blood sample taken ideally 30-60 minutes after the onset for tryptase testing, and samples may be analyzed by a local laboratory.

#### 4.6.3 Vital Signs and Physical Examination Variables

The following vital signs (VS) parameters will be collected:

- Systolic and diastolic blood pressure (mmHg)

- Pulse rate (bpm)
- Temperature (C)
- Respiratory rate (breaths/min)

Vital signs parameters will be collected as specified in the SoA ([Appendix 11.1](#)). On study treatment dosing days, i.e., Baseline (Day 1), Week 2 (Day 15), and Week 4 (Day 29), vital signs should be assessed before initiation of infusion; 15 ( $\pm$  5) minutes after the initiation of the infusion; 15 ( $\pm$  5) minutes after EOI, and 1 hour ( $\pm$  15 minutes) post EOI.

A complete physical examination will include, at a minimum, assessments of the skin, head and neck, cardiovascular, respiratory, gastrointestinal, and neurological systems. Measurement of weight, height, and BMI will be conducted only at baseline, unless any supplementary evaluations necessitate further measurements. All the assessment will be performed as specified in the SoA ([Appendix 11.1](#)).

A brief physical examination will include, at a minimum, assessments of the skin, lungs, cardiovascular system, and abdomen (liver and spleen). Symptom-directed physical examinations will be completed at each follow-up (including the extended follow-up) visit at the discretion of the investigator.

Investigators will be instructed to pay special attention to clinical signs related to previous serious illnesses. Unscheduled physical examinations can be conducted at the discretion of the PI or designee.

#### **4.6.4 12-Lead Electrocardiogram (ECG) Variables**

The following ECG parameters will be collected:

- Heart rate (bpm)
- PR interval (msec)
- QRS duration (msec)
- QT interval (msec)
- QTcB interval (msec)
- QTcF interval (msec)
- Overall interpretation

Triplicate ECG will be taken if there are any clinically significant abnormalities detected by the physician in a single ECG. The ECG assessment will be performed as specified in the SoA ([Appendix 11.1](#)).

#### **4.7 Pharmacokinetic (PK) Variables**

The blood samples will be collected at day 1/baseline (pre-dose and EOI), days 8, 15 (pre-dose and EOI), 29 (pre-dose and EOI), 43, 57, 85, 113/EOT, 141, and 169/EOS.

#### **4.8 Pharmacodynamic (PD) Variables**

## 4.9 Immunogenicity Variable

The variables include ADA status (positive or negative) as follows:

- Total participants negative in the ADA assay at all time points analyzed
- Total participants positive in the ADA assay at any time point analyzed
- Total participants with pre-existing ADA
- Total participants with treatment emergent response
- Total participants with treatment boosted response
  - *Pre-existing ADA*: Either an ADA positive response in the assay at baseline with all post first dose ADA results negative, OR a positive response at baseline with all post first dose ADA responses less than 4-fold over baseline titer levels.
  - *Treatment-boosted response*: Pre-existing ADA that is increased to a higher concentration (4-fold or higher level) after administration of therapeutic protein product.
  - *Treatment-emergent response*: ADA developed de novo (seroconversion) following administration of therapeutic protein product in a participant who lacked detectable pre-existing ADA
    - a. *Persistent response*: Treatment-emergent response detected at 2 or more sampling time points during the treatment (including follow-up period if any), where the first and last ADA-positive samples (irrespective of any negative samples in between) are separated by a period of 16 weeks or longer.

- b. *Indeterminate Response*: Treatment-emergent response with only the last collected sample positive in the ADA assay
- c. *Transient response*: Treatment emergent ADA positive assay response that is not considered persistent or indeterminate.

Blood sample for the immunogenicity analysis will be collected at Day 1/Baseline (pre-dose), days 15(pre-dose), 29 (pre-dose), 43, 57, 85, 113/EOT, 141, and 169/EOS.

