## 5.11 Analysis of Immunogenicity Data

The ADA variables will be summarized using descriptive statistics by treatment in the immunogenicity analysis set. Frequency tables of the proportion of participants developing ADA positivity in the ADA assay, pre-existing ADA, treatment-emergent, treatment-boosted, persistent, indeterminate and transient ADA responses will be presented as absolute occurrence (n) and percent of participants (%), presented by treatment groups.

A listing of ADA data will be provided. The number and percentage of participants with ADA positive at each visit will be presented in the listing. The percentage will be based on the number of participants with ADA assessment at each visit.

The following summaries will be performed on the immunogenicity analysis set:

- Number (%) of patients negative ADA at all the time points analyzed by treatment group
- Number (%) of patients ADA positive at time points analyzed by treatment group
- Number (%) of patients with pre-existing ADA, treatment-emergent ADA, and treatment boosted ADA response by treatment group
- Number (%) of patients with persistent, transient and indeterminate treatment-emergent ADA response by treatment group
- Descriptive statistics of PK concentration in ADA positive and ADA negative participants by treatment group
- Descriptive statistics of dose adjusted PK concentration in ADA positive and ADA negative participants

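### SAP 4.9 builds the treatment-boosted ADA class on a pre-existing term that already excludes a 4-fold rise, so read literally the class is empty; on the likely reading the pre-existing row is not baseline positivity (minor)

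*SAP*

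**What the plan says.** SAP 4.9 (Immunogenicity Variable) sets out three ADA classes.

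- **Pre-existing ADA** has two limbs. The first is "Either an ADA positive response in the assay at baseline with all post first dose ADA results negative". The second is "a positive response at baseline with all post first dose ADA responses less than 4-fold over baseline titer levels".
- **Treatment-boosted response** is "Pre-existing ADA that is increased to a higher concentration (4-fold or higher level) after administration of therapeutic protein product".
- **Treatment-emergent response** is "ADA developed de novo (seroconversion) following administration of therapeutic protein product in a participant who lacked detectable pre-existing ADA". It is subdivided into persistent, indeterminate and transient.

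The same section lists a total for each class, plus totals for participants negative at all time points and positive at any time point. On sampling it says: "Blood sample for the immunogenicity analysis will be collected at Day 1/Baseline (pre-dose), days 15(pre-dose), 29 (pre-dose), 43, 57, 85, 113/EOT, 141, and 169/EOS". That is one baseline and eight post-dose samples.

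SAP 5.11 (Analysis of Immunogenicity Data) plans the summary "Number (%) of patients with pre-existing ADA, treatment-emergent ADA, and treatment boosted ADA response by treatment group". It has no summary row for ADA positive at baseline. It does say of the ADA listing: "The number and percentage of participants with ADA positive at each visit will be presented in the listing".

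**The concern.** Pre-existing ADA is set out as a defined term, and part of its definition is that no post-dose result reaches 4-fold over baseline. The boosted definition then starts from that term and requires a rise of 4-fold or more. A programmer who follows the text exactly would get zero boosted participants whatever the data showed. A participant whose existing antibodies were boosted by the drug would drop out of the class table.

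A milder problem remains if the programmer reads past the contradiction. The row for pre-existing ADA keeps its own narrow definition and so leaves out the boosted participants. With no separate row for baseline positivity, a reader of the table could easily take the pre-existing row for that figure.

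At stake is whether the class rows in SAP 5.11 report what their labels suggest. Immunogenicity is an exploratory objective (SAP 1.2.3), but a boosted response is one of the findings these tables exist to show.

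**Working it through.** The plan states no figure on this point, so there is nothing to reproduce. The check is one of set logic.

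**Inputs.** The three definitions and the eight post-dose samples (Days 15, 29, 43, 57, 85, 113, 141 and 169) come from SAP 4.9. The planned cohort sizes of 6 and 24 come from SAP 2.1.

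**Coding.** For a baseline-positive participant, each post-dose sample is coded N (negative), L (positive, below 4-fold of baseline titer) or H (positive, 4-fold or more). A mixture of N and L is taken to satisfy the second pre-existing limb. The number of possible patterns is 3^8 = 6,561.

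**Literal reading.**
- Pre-existing: no H at any sample, 2^8 = 256 patterns.
- Boosted: pre-existing (no H) and at least one H, 0 patterns.
- Treatment-emergent: requires no detectable ADA at baseline, 0 patterns.
- In none of the three classes: 6,561 − 256 = 6,305 patterns, which are all those with at least one H.

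These are counts of logical possibilities, not expected frequencies. They show that every baseline-positive participant with a 4-fold or greater rise is left unclassified and appears only in the positive-at-any-time-point total.

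**Likely intended reading** (boosted means ADA present at baseline, then a 4-fold or greater rise).
- Pre-existing: 256 patterns.
- Boosted: 6,305 patterns.
- Sum: 256 + 6,305 = 6,561, so the two classes do not overlap and together cover all baseline positives.
- Pre-existing row = baseline positives − boosted.

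**Illustration with assumed counts.** Take 30 participants, 3 of them positive at baseline.

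| Participants with a 4-fold or greater rise | Pre-existing row | Boosted row, literal | Boosted row, intended | Positive at baseline |
|---|---|---|---|---|
| 0 | 3/30 (10.0%) | 0 | 0 | 3/30 (10.0%) |
| 1 | 2/30 (6.7%) | 0 | 1 | 3/30 (10.0%) |

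**Size per participant.** One participant is 1/6 = 16.7% of Cohort 1 or 1/24 = 4.2% of Cohort 2. The documents give no baseline ADA prevalence and no boosting rate. Any probability of seeing such a participant would rest wholly on assumed rates, so none is given.

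**The case against.** The strongest reply is that this is a slip of one phrase. The below-4-fold and 4-fold-or-higher limits are exact complements, and both SAP 4.9 and SAP 5.11 plan to count boosted participants, so the authors plainly expected that the class could be filled. Read in the ordinary sense of ADA present before dosing, the definitions form a coherent split. This stands as the likely intent, and it is the main reason the point is minor. It does not remove the point, because the same term then carries two meanings in adjacent definitions and the programmer must choose between them.

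It can also be said that the pre-existing row never claims to be baseline positivity, and that the Day 1 figure will be in the by-visit ADA listing. Both are correct. Nothing is lost from the data, and the remaining risk is that the summary row is misread.

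A reader might go further and infer that boosted participants would be counted as treatment-emergent, inflating that rate and its persistent and transient breakdown. The argument would be that someone outside the defined pre-existing class is "in a participant who lacked detectable pre-existing ADA". The full definition does not support this. It requires ADA that developed de novo, by seroconversion, and the absence of detectable ADA beforehand. A baseline-positive participant fails both conditions. The supported consequence is that the participant is unclassified.

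**Conclusion.** The contradiction is in the text, and its severity is minor. On the literal reading the boosted row is empty by construction, and baseline-positive participants with a 4-fold or greater rise fall in no class. On the likely reading the boosted row is sound, and the pre-existing row falls short of baseline positivity by exactly the number boosted.

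On either reading, no row is wrong or open to misreading on this account unless at least one baseline-positive participant has a 4-fold or greater rise. How often that will happen cannot be judged from the documents.

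The effect is confined to descriptive, exploratory ADA class tables. The summaries of PK by ADA status in SAP 5.9 and 5.11 use positive or negative status and do not depend on these classes. The TEAE primary endpoint and the SALT secondary endpoint are untouched. It would be too strong to say that the boosted class will be empty in the reported analysis, since that depends on a literal reading the authors probably did not intend.

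**What to change.** Make three wording changes in SAP 4.9 and carry them into the SAP 5.11 summaries:

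1. **Treatment-boosted:** ADA positive at baseline with at least one post-dose titer 4-fold or more over the baseline titer.
2. **Treatment-emergent:** ADA negative at baseline and positive at any post-dose sample.
3. **Existing pre-existing row:** keep the definition and label it as pre-existing, not boosted. Among participants with a baseline and at least one post-dose ADA result, this row plus the boosted row then equals baseline positivity.

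A separate row for ADA positive at baseline, with the two subclasses beneath it, would help the reader but is optional. The cost is a few lines of SAP text and a table label. No new samples, data or analyses are needed.

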The extended follow-up period after EOS consists of two visits: Week 30 (Day 211) and Week 36 (Day 253).

The schedule of assessments (SoA) at each visit is summarized in [Table 1](#). Assessments of efficacy, safety will be conducted throughout this study (until extended follow-up period post EOS) and PK, PD, and immunogenicity data will be collected until the end of EOS visit.

Participants who discontinue treatment early (before completing the 4-week dosing period) should continue with all the remaining study visits.

Participants who withdraw from the study any time before the Week 16 visit should complete the Week 16 (Day 113)/EOT visit at withdrawal.

Participants who withdraw from study early during the follow-up period should complete the Week 24 (Day 169)/EOS visit at withdrawal.

Participants who discontinue early after the Week 24/EOS visit but before the Week 36 visit should complete Week 36 (Day 253) visit at withdrawal.

A participant who withdraws from the study prior to receiving two doses of study treatment (i.e., completing the Week 2 visit) for reasons other than AEs will be replaced.

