7.4 Pharmacokinetic and Immunogenicity Assessments

Blood will be collected to describe the PK and immunogenicity profiles of IMG-007 as outlined in [Table 5](#).

Participants with signs of any potential immune response to IMG-007 will be closely monitored with clinical evaluations. The PK and anti-drug antibody (ADA) samples may be collected at unscheduled visits for further evaluation.

Details concerning handling of PK and ADA serum samples, including labeling and shipping instructions, will be provided in the Laboratory Manual. The actual time each sample was collected will be captured to the nearest minute in the eCRF and recorded in the database.

Samples will be shipped to laboratory where samples will be analyzed for serum IMG-007 concentrations using a validated method.

Validated screening and confirmatory assays will be employed to detect ADAs at multiple timepoints throughout the study.

The immunogenicity evaluation will utilize a risk-based immunogenicity strategy ([Bai et al 2012](#); [Rosenberg et al 2004](#)) to characterize ADA responses to IMG-007 in support of the clinical development program.

Table 5 PK and ADA Sampling Schema

Dose No.	Day	Pre-/Post-dose	PK sampling time	ADA sampling time	Sampling Window
1	1	Pre-dose	0	0	-60 mins
	1	Post-dose	EOI	--	+10 mins
	8	Post-dose	7 days post-dose	--	±3 days
2	15	Pre-dose	0	0	-60 mins
	15	Post-dose	EOI	--	+10 mins
3	29	Pre-dose	0	0	-60 mins
	29	Post-dose	EOI	--	+10 mins
	43	Post-dose	14 days post-dose	14 days post-dose	±3 days
	57	Post-dose	28 days post-dose	28 days post-dose	±3 days
	85	Post-dose	56 days post-dose	56 days post-dose	±3 days
	113/EOT	Post-dose	84 days post-dose	84 days post-dose	±3 days
	141	Post-dose	112 days post-dose	112 days post-dose	±3 days
	169/EOS	Post-dose	140 days post-dose	140 days post-dose	±3 days

Abbreviations: ADA = anti-drug antibody; EOI = end of Infusion; EOT = end of treatment; EOS = end of study; PK = pharmacokinetic

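### SAP 4.9 classes an ADA response still positive at the last sample as transient when it spans under 16 weeks, unless that sample is the only positive one

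*SAP*

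**What the plan says.** SAP 4.9 sorts treatment-emergent ADA responses into three classes.

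- **Persistent**: positive at two or more time points, "where the first and last ADA-positive samples (irrespective of any negative samples in between) are separated by a period of 16 weeks or longer".
- **Indeterminate**: "Treatment-emergent response with only the last collected sample positive in the ADA assay".
- **Transient**: "Treatment emergent ADA positive assay response that is not considered persistent or indeterminate".

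The same section lists the ADA samples: Day 1 before dosing, then Days 15, 29, 43, 57, 85, 113 (EOT), 141 and 169 (EOS). Protocol Table 5 gives the same days, with windows of ±3 days from Day 43 onward. No ADA sample is scheduled in the extended follow-up, because under Protocol 4.1.2 "PK, PD, and immunogenicity data will be collected until the end of EOS visit".

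Protocol 4.1.2 also covers withdrawal, and its rule for the treatment period reads: "Participants who withdraw from the study any time before the Week 16 visit should complete the Week 16 (Day 113)/EOT visit at withdrawal". Someone who leaves later, in the follow-up period, has the EOS visit brought forward in the same way. Participants who only stop treatment stay on the full visit schedule. Protocol 7.4 adds that PK and ADA "samples may be collected at unscheduled visits for further evaluation" when there are signs of an immune response.

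SAP 5.11 plans to report "Number (%) of patients with persistent, transient and indeterminate treatment-emergent ADA response by treatment group", together with a listing of the ADA data.

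**The concern.** An indeterminate class exists for responses whose duration cannot be judged because sampling ended. As written, it catches only one such case, a lone positive at the final sample. Two or more positives that run up to the final sample but span less than 16 weeks fall into the residual class. So a participant with more evidence of a continuing response moves from indeterminate to transient, a label that suggests the response went away.

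The transient count in the SAP 5.11 table would then mix two groups: responses that were negative at the last sample, and responses still positive when sampling stopped. In cohorts of 6 and 24, one relabelled participant is 1/6 or 1/24 of the cohort.

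**Working it through.** The plan gives no figure of its own on this point, so the check applies the three definitions literally to every possible result pattern.

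**Inputs.** Post-baseline ADA days 15, 29, 43, 57, 85, 113, 141 and 169 (SAP 4.9). Persistence threshold 16 weeks × 7 = 112 days. Baseline negative and at least one later positive, so that the response is treatment-emergent. Nominal days, with every scheduled sample up to the last one taken.

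**Rule as written.** Let F and L be the days of the first and last positive.
- Persistent: at least two positives and L − F ≥ 112.
- Indeterminate: the only positive is the last collected sample.
- Transient: all else.

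**Rule as proposed.** Persistent is unchanged. If not persistent, a positive last sample is indeterminate and a negative last sample is transient.

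**Full schedule.** There are 2^8 − 1 = 255 positive patterns, of which 2^7 = 128 are positive on Day 169. Of these 128, 120 are persistent, 1 is indeterminate (Day 169 only) and 7 are transient:

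| First positive | Span to Day 169 | Patterns | Positive at every sample from onset |
|---|---|---|---|
| Day 85 | 84 days | 4 | 1 |
| Day 113 | 56 days | 2 | 1 |
| Day 141 | 28 days | 1 | 1 |

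The other 4 have a negative in between, which the persistent rule would itself ignore.

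**Shorter follow-up.** The same count with an earlier last sample, shown as persistent/indeterminate/transient:

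| Last sample | Patterns | As written | As proposed | Moved | Of these, uninterrupted |
|---|---|---|---|---|---|
| Day 169 | 255 | 168/1/86 | 168/8/79 | 7 | 3 |
| Day 141 | 127 | 48/1/78 | 48/16/63 | 15 | 4 |
| Day 113 | 63 | 0/1/62 | 0/32/31 | 31 | 5 |
| Day 85 | 31 | 0/1/30 | 0/16/15 | 15 | 4 |

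**Why persistent disappears at Day 113.** The longest span is 113 − 15 = 98 days. With ±3 days at both ends it is 116 − 12 = 104 days. Both are under 112, so a participant positive at every post-baseline sample is transient.

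**Patterns on the threshold.** Day 57 to Day 169 is exactly 112 days on nominal days. With ±3-day windows it runs from 166 − 60 = 106 to 172 − 54 = 118, so it can fall on either side. There are 2^3 = 8 such patterns, and all are positive at the last sample. Day 29 to Day 141 is also exactly 112 days. That gives 2^4 = 16 patterns on the full schedule, all negative on Day 169. If all 24 fell short, the full-schedule result would be 144/1/110 as written and 144/16/95 as proposed, so 15 patterns would move instead of 7.

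**The case against.** The strongest reply is that the three classes are explicit, exclusive and exhaustive. Transient is openly a residual, and neither document says that it means resolved. A reader with the definition next to the table is not misled, and the listing shows each case. That is right about the logic but does not explain the ordering: a lone final positive is set aside as undetermined, and a run of positives ending at the same sample is not. A listing also does not correct a summary count.

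A second reply is that the consequence is small, and this stands. The split is descriptive and exploratory, and it applies only to treatment-emergent responders in a study of about 30. No endpoint or planned decision uses it. On nominal days a completer must first turn positive at Day 85 or later, at least 56 days after the last nominal dose on Day 29, and be positive again on Day 169.

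Three limits on the counts also stand.
- They weight every pattern equally, so they show which cases are affected and not how many participants.
- They hold on nominal days. A withdrawal visit often falls off that grid, and the Day 141 row mainly fits withdrawal near that day or a missed EOS visit.
- The statement that persistent is out of reach by Day 113 holds for visits within ±3 days. The SAP's ADA analysis window for Week 16 (Appendix 11.3) runs to Day 127, and Day 15 to Day 127 is 112 days. An unscheduled sample could also change a single case.

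Finally, one negative at the last sample does not prove resolution, since more sampling might have found a later positive. This is true, but the proposed split claims only the last observed status, which is more than the present residual class can claim.

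**Conclusion.** The concern holds and is minor. Read literally, SAP 4.9 reports as transient any treatment-emergent response that is still positive at the last sample, has an earlier positive, and spans less than 112 days. No other visible rule in the protocol or SAP corrects this. On the full nominal schedule it covers 7 of 255 patterns, or up to 15 if the patterns at exactly 112 days fall short. With a last sample on Day 113 it covers 31 of 63.

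The documents give no ADA incidence or distribution of onset times, so the number of participants affected cannot be estimated and may be zero. ADA incidence, treatment-emergent and treatment-boosted counts, and PK by ADA status are unaffected.

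**What to change.** In SAP 4.9, leave persistent as it is and reword the other two classes:

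- **Indeterminate**: a treatment-emergent response that does not meet the persistent criterion and is positive at the last collected sample.
- **Transient**: a treatment-emergent response that does not meet the persistent criterion and is negative at the last collected sample.

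The classes stay exclusive and exhaustive, and the persistent count does not change. The cost is two lines of SAP wording, with no new samples or data. The table may show more indeterminate and fewer transient responses than under the present wording.
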